Study Protocol

Official Title: Effect of Polydeoxyribonucleotide (PDRN) on Healing and Fatty Degeneration of Rotator Cuff in Human

Document Date: March 19th, 2019

Background: Polydeoxyribonucleotide is a tissue regeneration activator. It binds adenosine A2A receptor and stimulate VEGF(vascular endothelial growth factor) synthesis and stimulate collagen synthesis. Nowadays, a lot of arthroscopic rotator cuff repairs are being performed. but the failure rate of rotator cuff repair is considerably high. Therefore, this study is to evaluate the effect of polydeoxyribonucleotide for healing and fatty degeneration of rotator cuff.

Objective: This study is to evaluate the effect of polydeoxyribonucleotide (PDRN) for healing and fatty degeneration of rotator cuff.

Methods: We will enroll 130 patients with rotator cuff tear who will undergo arthroscopic rotator cuff repair. 130 patients will be classified into two group. One group (PDRN) will be injected at the repaired cuff with 3cc polydeoxyribonucleotide just after surgery and be injected with another 3ml polydeoxyribonucleotide under ultrasound guidance 2 weeks after the surgery. The other group (CONTROL) will be injected with 3ml normal saline in the same manner.

Visual analog scale (VAS) of pain and other functional scores of the two group will be checked preoperatively and postoperative 3, 6, 12, 24 months. Growth factors (VEGF, FGF, IGF) will be checked preoperatively and postoperative 1h, 2 days, 2 weeks, 6 weeks, 3, 6 months. Follow up MRI will be checked at postoperative 6 months. The parameters will be compared using statistical analysis.

[figure not shown]

Fig 1. Flow diagram

Statistical analysis plan

In a previous similar study, prior power analysis was performed to determine the study sample size to provide a statistical power of 80% at an α level of .05. A sample size of 47 patients per group was calculated to be sufficient to detect a minimum 5-point difference in the Constant score at the end of 2 years with 10% probable loss of the data. We plan to follow up more than 50 participant in the each two groups. And we compared the score improvement sequentially between the two groups using Mann-Whitney test or independent t test according to the normality.

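### The SAP tests unadjusted score improvement; adjusting for the preoperative score by ANCOVA would usually be more precise with the same data

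*Combined protocol and SAP*

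**What the plan says.** The Methods paragraph provides for a baseline: "functional scores of the two group will be checked preoperatively and postoperative 3, 6, 12, 24 months". The Statistical analysis plan then gives a single comparison: "we compared the score improvement sequentially between the two groups using Mann-Whitney test or independent t test", with the choice between the two tests depending on normality. It mentions no covariate, regression model, ANCOVA or mixed model.

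The sample-size statement is carried over from a previous study. It assumes "a statistical power of 80% at an α level of .05" and 47 patients per group, with an allowance of 10% for lost data, in order to "detect a minimum 5-point difference in the Constant score at the end of 2 years". It gives no SD and no correlation between preoperative and later scores. It does not say whether the 5 points refer to the 2-year score or to the change from baseline.

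On numbers, the plan says "We plan to follow up more than 50 participant in the each two groups". On allocation, the readable text says only "130 patients will be classified into two group"; the flow diagram is not available.

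**The concern.** Testing improvement amounts to regressing the final score on the preoperative score with the slope forced to 1. When the true slope is below 1, which is the case for any correlation below 1 with equal SDs, subtraction over-corrects and adds baseline noise to the outcome. Two things follow under random allocation:

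- **Precision.** The treatment difference has a wider confidence interval than the same patients could give.
- **Chance imbalance.** With equal SDs, a chance difference in preoperative score between the groups carries into the estimated effect by (1 − r) times that difference.

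At stake is power for the 5-point Constant-score difference, the only target with a sample-size basis. The validity of the test under randomisation is not in question.

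**Working it through.** **Inputs from the document:** difference 5 points, alpha 0.05, power 80%, 47 per group including 10% loss, more than 50 per group followed up, 130 enrolled.

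**Assumptions:** two-sided test, 1:1 random allocation, normal scores; r and the SD ratio varied over a range. Power is from the noncentral t distribution.

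**Step 1. The plan's own figure.** The 47 cannot be reproduced because no SD is given. Solving backwards for 80% power:

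- 47 less 10% is 47 × 0.9 = 42.3 evaluable per group, giving SD = 8.11.
- If all 47 are evaluable, SD = 8.56.

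This only shows what SD the figure implies; it does not confirm it.

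**Step 2. Variances with equal pre and post SD.**

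- Change score: 2(1 − r)·SD²
- ANCOVA: (1 − r²)·SD², times 1 + 1/(2n − 4) for estimating the slope. At n = 50 this factor is 1 + 1/96 = 1.010; at n = 58 it is 1.009.
- Ratio change/ANCOVA before the slope cost: 2(1 − r)/(1 − r²) = 2/(1 + r)

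At r = 0.3: 2/1.3 = 1.54, and 1.54/1.010 = 1.52, so 50 × 1.52 = 76 per group are needed on change to match ANCOVA with 50. At r = 0.5: 2/1.5 = 1.33, net 1.32, so 50 × 1.32 = 66.

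**Step 3. Power if 8.11 is the SD of the 2-year score.** For example, at r = 0.3 the SD of change is 8.11 × √1.4 = 9.60 and the ANCOVA residual SD is 8.11 × √0.91 = 7.74. The 58 per group is 65 × 0.9 = 58.5, rounded down.

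| r | Ratio, net (n = 50) | Change, n = 50 | ANCOVA, n = 50 | Change, n = 58 | ANCOVA, n = 58 |
|---|---|---|---|---|---|
| 0.2 | 1.65 | 68% | 87% | 74% | 92% |
| 0.3 | 1.52 | 73% | 89% | 79% | 93% |
| 0.4 | 1.41 | 80% | 91% | 85% | 95% |
| 0.5 | 1.32 | 86% | 94% | 91% | 97% |
| 0.6 | 1.24 | 93% | 97% | 96% | 98% |
| 0.7 | 1.16 | 98% | 99% | 99% | 99.6% |

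The change score falls below 80% only when r is under about 0.41 (50 per group) or 0.31 (58 per group). A simulation with normal data at 50 per group agreed to within about one percentage point. In the same simulation Mann-Whitney on change gave 72% at r = 0.3 and 85% at r = 0.5.

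**Step 4. Power if 8.11 is already the SD of change.** At 50 per group the planned test has 86%. ANCOVA has 97.5% at r = 0.2, 94% at r = 0.5 and 91% at r = 0.7.

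**Step 5. Unequal SDs.** With baseline SD equal to k times the final SD, the change variance is SD²(1 + k² − 2rk). Net ratios change/ANCOVA at 50 per group:

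| k | r = 0.2 | r = 0.5 | r = 0.7 |
|---|---|---|---|
| 0.8 | 1.36 | 1.11 | 1.01 |
| 1 | 1.65 | 1.32 | 1.16 |
| 1.25 | 2.13 | 1.73 | 1.58 |

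At k = 0.5 and r = 0.5 the ratio is 0.99: the true slope is 0.5/0.5 = 1, and ANCOVA pays only the 1% slope cost.

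**Step 6. Larger SD.** If the final-score SD is 10 (equal SDs, 50 per group), power for change against ANCOVA is 55% vs 73% at r = 0.3 and 70% vs 81% at r = 0.5. If it is 12, the figures are 41% vs 58% and 54% vs 66%. ANCOVA therefore does not by itself secure 80%.

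**The case against.** The strongest reply is that nothing here is an error. Both planned tests control the type I error under random allocation, and the loss of planned power appears only in some scenarios. If the implied SD is that of change, which is the scale the SAP analyses, the planned test already has 86% at 50 per group and 91% at 58, and 50 is a floor. The inputs that set the size of the gain are absent, so any table of power looks firmer than the document allows. All of this stands, and it limits the point to one of efficiency with an unfixed size. It does not remove the point: within the ranges examined, the worst result for ANCOVA is a loss of about 1% of variance.

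A second reply is that the efficiency argument needs randomisation, which the readable text does not state. That also stands. Without randomisation, change scores and ANCOVA can estimate different quantities, so the choice matters more and the allocation method has to be stated before either is fixed.

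Third, the plan names no primary endpoint, and it compares scores at several visits. The Constant score is nevertheless the only outcome with a sample-size basis, and the same model can be used at each visit. The closed-form ratio applies to the t test; the Mann-Whitney comparison was checked only on normal data, not on the non-normal data for which the SAP reserves that test.

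**Conclusion.** The point holds as an improvement in precision that the plan should adopt, not as a flaw that invalidates the analysis. With random allocation and equal SDs, the unadjusted change score has 1.16 to 1.65 times the variance of ANCOVA for r from 0.7 down to 0.2, at 50 evaluable per group. The gain shrinks towards nothing as the slope of final on preoperative score approaches 1, and grows when the baseline SD exceeds the final SD. The power figures rest on an SD back-solved from the borrowed 47 per group and illustrate the effect only. Confidence in the direction is high under randomisation; confidence in the size is limited by the missing SD and correlation.

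**What to change.** In the Statistical analysis plan:

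1. Provided allocation is random, make the main analysis of the Constant score an ANCOVA of the 24-month score on treatment group and preoperative score, and report the adjusted mean difference with a 95% CI.
2. Use the same model for VAS and the other functional scores, and at the earlier visits if these are compared. Report mean improvement descriptively.
3. Keep a rank-based analysis as a prespecified sensitivity check for non-normal scores.
4. State how patients are allocated, the SD and correlation assumed, and whether the 5 points refer to the 2-year score or to change.

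The cost is a few sentences, with no new data or patients. Estimating the slope uses one degree of freedom and about 1% of variance.

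### Read as written, the 24-month functional-score test makes no use of lost patients' earlier scores; a repeated-measures model on visits already scheduled would use them, for a modest gain

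*Combined protocol and SAP*

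**What the plan says.** The Methods paragraph sets the size and the visits: "We will enroll 130 patients with rotator cuff tear who will undergo arthroscopic rotator cuff repair", and pain and "other functional scores of the two group will be checked preoperatively and postoperative 3, 6, 12, 24 months". Imaging is separate: "Follow up MRI will be checked at postoperative 6 months".

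The Statistical analysis plan section borrows its sizing from a previous study, which aimed "to provide a statistical power of 80% at an α level of .05" and needed 47 per group for a "minimum 5-point difference in the Constant score at the end of 2 years with 10% probable loss of the data". It then sets a follow-up target, "We plan to follow up more than 50 participant in the each two groups", and ends with the only analysis named: "we compared the score improvement sequentially between the two groups using Mann-Whitney test or independent t test according to the normality".

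The visible text has no rule for missing scores, no analysis set and no model that joins the visits. The flow diagram is not shown and may add detail. The Constant score is named only in the borrowed calculation, not in the visit schedule.

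**The concern.** A two-sample test of improvement at 24 months needs a 24-month score. A patient seen at 3, 6 and 12 months and then lost contributes to the tests at those visits but not to the one at 24 months, which is the time point of the borrowed sizing. That calculation itself expects some loss.

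Two things are at stake. The first is precision: earlier scores predict the later one, so leaving them out wastes information even when loss is harmless. The second is bias: if patients doing poorly at 12 months drop out more often in one group, the patients seen at 24 months no longer compare like with like. A likelihood-based model that uses all scheduled scores recovers some of the precision, and it removes the bias when loss depends only on scores already seen.

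**Working it through.** **Inputs from the plan.** 130 enrolled; more than 50 per group to be followed; 47 per group in the borrowed calculation; 5 points; 80% power; α 0.05; 10% loss; scores at 3, 6, 12 and 24 months.

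**Assumptions.** Two-sided test, 65 per group, correlations between visits of 0.3 to 0.7 (exchangeable or first-order autoregressive), all loss after 12 months, and the loss patterns below.

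**The plan's figure.** The 47 cannot be verified because no SD is given, so I solve for it. 47 × 0.9 = 42.3, so about 42 evaluable. SD = 5 × √(42/2) / (1.960 + 0.842) = 8.18 by the normal approximation, or about 8.1 with the t distribution. I use 8.1.

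**Two loss levels.** The only stated rate is 10%. The follow-up target gives a second, illustrative level: 130 − 2 × 51 = 28, and 28/130 = 14/65 = 21.5%.

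**Precision, loss unrelated to outcome.** With R² for the 24-month score on the three earlier scores and a fraction f lost, the variance ratio (model to test) is 1 − R² × f in large samples. R² is r² if autoregressive and 3r²/(1 + 2r) if exchangeable. Over r = 0.3 to 0.7 it runs from 0.09 (autoregressive, 0.3) to 0.61 (exchangeable, 0.7).

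| Loss | R² = 0.09 | R² = 0.61 |
|---|---|---|
| 10% | 0.991 | 0.939 |
| 14 of 65 | 0.981 | 0.868 |

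The variance falls by about 1% to 6% at 10% loss and by about 2% to 13% at 14 of 65. The latter is like regaining 51/0.981 − 51 ≈ 1 to 51/0.868 − 51 ≈ 8 patients per group.

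**Bias, loss driven by 12-month improvement.** Suppose the k of 65 with the lowest 12-month values are lost, ranked after adding noise of s SDs. The mean of those left rises by h(k) = φ(z)/(1 − k/65) SDs, where z is the normal quantile of k/65. The bias of the 24-month difference is about SD × r × [h(k1) − h(k2)] / √(1 + s²).

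| Lost per group | h(k1) − h(k2) | Smallest (r = 0.3, s = 2) | Largest (r = 0.7, s = 0) |
|---|---|---|---|
| 8 vs 5 | 0.232 − 0.156 = 0.076 | 0.08 | 0.43 |
| 9 vs 4 | 0.256 − 0.130 = 0.127 | 0.14 | 0.72 |
| 14 vs 7 | 0.373 − 0.208 = 0.165 | 0.18 | 0.94 |

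The first two rows are 13 of 130, or 10% overall: about 0.1 to 0.7 points. The third gives about 0.2 to 0.95 points. Simulation agrees with these figures, and the likelihood estimate with unstructured covariance was within simulation error of zero. The simulations had no baseline covariate.

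**Equal numbers lost.** With the same mechanism in both groups the bias is zero. With different mechanisms it is not: 23% lost in each group, r = 0.7, and one group's loss tied to the 12-month score at a log-odds of 1 per SD moved a true 5 to about 3.9 or 6.2 among those seen. The likelihood estimate stayed at 5.0.

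**Loss driven by the unseen 24-month score.** At 14 vs 7 with r = 0.5 to 0.7 and s of 0 to 1, the test is biased by 0.93 to 1.34 points and the model by 0.40 to 1.09. The model removes 18% to 57%.

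**The case against.** The plan is silent on missing scores; it does not choose completers. A reader might infer that the trial has specified a completers-only analysis. The documents do not say so: imputation is neither planned nor excluded, the flow diagram is missing, and even the visit-by-visit reading of the comparison is the likely sense, not a stated one. This stands, so the point holds only for the text as written.

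The importance of the 24-month score is also inferred. The objective is healing and fatty degeneration, MRI is at 6 months, and no primary endpoint is declared. The functional scores may be secondary. This stands and lowers the weight of the point.

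A reader might take the follow-up target as acceptance of 21.5% loss at 24 months. The text does not tie that target to a visit, and it is neither a forecast nor a cap.

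The loss patterns are assumptions, and lower correlation or weaker selection shrinks the figures. This stands, which is why the ranges include correlation 0.3, noise of 2 SD and 10% loss. Placing all loss after 12 months is favourable to the model.

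Finally, separate tests with a stated missing-data rule and sensitivity analysis would also close the gap, and swapping in a normal-theory model would drop the plan's provision for non-normal scores. The first is a fair alternative, though it would still need a method to draw on the earlier scores. The second is met in the wording proposed below.

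**Conclusion.** The point holds in a limited form. The only stated analysis of the functional scores does not draw on lost patients' earlier scores at 24 months, and a model on visits already scheduled would.

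At the documents' own 10% loss, the gain is a variance reduction of about 1% to 6%. The bias avoided is about 0.1 to 0.7 points, or 2% to 14% of the 5-point difference, and only if loss depends on 12-month improvement and differs by group. At 14 of 65 lost per group the variance reduction is about 2% to 13%, and at 14 vs 7 the bias is about 0.2 to 0.95 points. These figures rest on the back-solved SD, 65 per group, the assumed correlations and the assumed loss patterns.

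The documents do not show that the 24-month result will be biased, that the trial lacks power, or that the false-positive rate is inflated, and none of these is claimed. The 6-month MRI is outside the point. This is a change to consider, not a defect that undermines the trial.

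**What to change.** For the functional scores, replace the separate two-sample tests as the main analysis with wording such as:

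*Scores at 3, 6, 12 and 24 months will be analysed with a mixed model for repeated measures (unstructured covariance), including all allocated patients with at least one post-operative score, in their assigned group. Terms are group, visit, group-by-visit, preoperative score and preoperative score-by-visit. The 24-month contrast will be reported with a 95% CI. If residuals are clearly non-normal, robust or bootstrap standard errors will be used. The Mann-Whitney test at each visit is supportive. Loss will be reported by group and visit. A sensitivity analysis will set lost patients' 24-month Constant scores 5 and 10 points below the model's prediction, in each group alone and in both.*

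The two shifts are one and two times the 5-point difference in the borrowed sizing.

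The cost is SAP wording and slightly more analysis work, with no new visits or patients. The model assumes that loss depends only on observed data, so it corrects only part of the bias if loss depends on the unseen 24-month score; the sensitivity analysis is there for that reason. Patients lost before 3 months add nothing to the model.

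### Scores are compared at four visits with no primary test or multiplicity rule, so the chance of some false significant difference exceeds 5%: about 11-16% for one score and 23-38% for three, under assumed correlations

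*Combined protocol and SAP*

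**What the plan says.** Methods sets the measurement schedule. Alongside VAS pain, "other functional scores of the two group will be checked preoperatively and postoperative 3, 6, 12, 24 months". Each score therefore has one baseline value and four postoperative values. The functional scores are not named or counted there.

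The Statistical analysis plan is one paragraph. Its first part reports the sizing of an earlier study, designed to "provide a statistical power of 80% at an α level of .05". That study's target was to "detect a minimum 5-point difference in the Constant score at the end of 2 years", and "A sample size of 47 patients per group was calculated to be sufficient" after allowing for 10% loss. This trial then aims to follow more than 50 patients per group.

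The analysis rule is the closing sentence: "we compared the score improvement sequentially between the two groups", "using Mann-Whitney test or independent t test according to the normality".

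The text names no primary score and no primary visit. It gives no testing order, no adjustment for multiple tests, no sidedness, and no significance level for this trial's own comparisons.

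**The concern.** The sizing concerns one score at one time. The analysis sentence neither names that comparison nor gives it priority over the others. An error rate chosen for one test does not cover a set of tests, and the plan describes a set: four visits for each score, and more than one score.

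Followed as written, a significant result for any score at any visit could be presented as an effect of PDRN, and no prespecified rule would mark it as exploratory. A reader of the results could not tell whether a reported difference was the planned test or the most favourable of many.

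The four improvements for a given score also share one preoperative value, so a chance baseline difference can recur from visit to visit and look like replication. That affects interpretation only. It is not a further source of false positives.

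**Working it through.** **1. Inputs from the documents.** Four postoperative visits (Methods). VAS pain plus a plural of other functional scores (Methods). α = .05, 80% power, a 5-point Constant difference at 2 years, 47 per group with 10% loss, and more than 50 per group to be followed (Statistical analysis plan).

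**2. Inputs assumed.** Each test is two-sided at .05. Three scores are tested, which is VAS plus the smallest plural. Correlation is 0.5-0.8 between visits and 0.3-0.7 between scores. There is no true effect, and the groups differ only by chance.

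**3. The plan's own figure.** No SD is given, so 47 can only be back-solved. With n = 2(1.96 + 0.842)² × SD² / 5², an SD of 8.1 gives 41.2, rounded up to 42, and 42 / 0.9 = 46.7, rounded up to 47. So 47 fits one two-sided .05 test with an SD of about 8.1. Other readings fit too: an SD of about 9.2 if one-sided, or about 8.65 if 47 is the number before loss. The figure is neither confirmed nor refuted. On any of these readings it belongs to a single comparison.

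**4. Upper limit, independent tests.**
- Either direction: 1 − 0.95⁴ = 18.5% (one score); 1 − 0.95¹² = 46.0% (three scores).
- Favouring PDRN only: 1 − 0.975⁴ = 9.6%; 1 − 0.975¹² = 26.2%.

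**5. Correlated tests.** Repeated measures on the same patients are correlated, which lowers these figures. I simulated standard normal test statistics with equal correlation between visits. For three scores, the correlation between different scores at different visits is the product of the two correlations. I counted draws with any |Z| > 1.96, and separately draws with any Z > 1.96.

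| Tests | Visit r | Score r | Any false difference | False difference favouring PDRN |
|---|---|---|---|---|
| 1 score × 4 visits | 0.5 | – | 15.6% | 7.8% |
| | 0.7 | – | 13.0% | 6.5% |
| | 0.8 | – | 11.4% | 5.7% |
| 3 scores × 4 visits | 0.5 | 0.3 | 38.4% | 19.8% |
| | 0.7 | 0.5 | 30.3% | 15.2% |
| | 0.8 | 0.7 | 23.4% | 11.7% |

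The single-test benchmarks are 5% (either direction) and 2.5% (favouring PDRN).

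**6. Checks.**
- t tests with 50 per group gave 15.4% (r = 0.5) and 11.5% (r = 0.8) for one score, so the normal approximation is adequate.
- Shared baseline: if all five measurements have equal variance (set to 1) and common correlation ρ, two improvements have covariance 1 − ρ and variance 2(1 − ρ), so their correlation is 0.5 whatever ρ is. With a baseline SD 1.5 times the follow-up SD, the correlation is 0.70-0.74 and the one-score rate 12.4-13.0%. Both lie inside the range above.
- If tests were one-sided at .05, the chance of a false benefit would be 10.6-14.4% (one score) and 20.2-33.6% (three scores).

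**7. What the remedies do.** A single test of the Constant score at 24 months stays at 5%. Splitting α over four visits (.0125 each) brings the one-score rate to 4.3% (r = 0.5) or 3.2% (r = 0.8), but costs power at 24 months. With the back-solved SD of 8.1 and 50 per group, 5 / (8.1 × √(2/50)) = 3.09. Power is then Φ(3.09 − 1.96) = 87% at .05 and Φ(3.09 − 2.50) = 72% at .0125.

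**The case against.** The strongest reply is that the sizing sentence already points to the Constant score at 2 years. Treat that as primary and its error is 5%, with the other comparisons secondary. This would be right if the plan said so. It does not: the sentence reports how a previous study was sized, and the analysis rule makes no distinction among scores or visits. Writing that declaration is the remedy.

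Several stronger readings are tempting, and the documents do not support them.

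- A reader might take 11-16% and 23-38% as the chance of a false PDRN benefit. Under two-sided tests those figures also count results where PDRN looks worse. The false-benefit chance is about half as large, and its benchmark is 2.5%.
- A reader might say that the plan prescribes .05 for every test. The .05 appears only in the account of the earlier study's power analysis. Applying it to each comparison is a fair inference, since no other level is offered, but it is not written.
- A reader might treat visit-by-visit testing of three scores as stated fact. The word used is ambiguous, and the number of scores comes from a plural. Visit by visit is the likeliest meaning. Testing as data mature, or one score after another, would still give several unadjusted tests.
- A reader might infer that the shared baseline inflates error further. It makes the tests positively correlated, which lowers the family rate compared with independence. Chance imbalance is already part of each test's 5%.

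It can also fairly be said that the stated Objective is healing and fatty degeneration, not function, and that other remedies would serve. Both points stand, and they limit the scope of the remedy.

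**Conclusion.** The concern holds in limited form. The plan implies several between-group tests of score improvement and has no rule that keeps the error over the set at 5%.

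Under the assumptions in step 2, the family error is roughly two to three times nominal for one score (11.4 / 5 = 2.3; 15.6 / 5 = 3.1) and five to eight times for three (23.4 / 5 = 4.7; 38.4 / 5 = 7.7). The chance of a false result in PDRN's favour rises by similar multiples of 2.5%.

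That the rate exceeds 5% needs only more than one imperfectly correlated test at .05. Its exact size depends on the number of scores, the correlations and the sidedness, none of which the documents give. The conclusion does not extend to the MRI or growth-factor analyses. The point should be settled before the groups are compared, but it does not call the design or the sample size into question.

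**What to change.** Replace the closing analysis sentence of the Statistical analysis plan with a statement that, for the functional scores:

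- Constant score improvement at 24 months is the single confirmatory comparison, tested at two-sided .05. It is the only score and time in the size statement.
- All other scores and visits, including VAS, are reported as between-group differences with 95% confidence intervals and no confirmatory significance claim.
- If the sponsor wants to claim Constant score differences at earlier visits, these are tested in a prespecified fixed order, only after the 24-month test succeeds, stopping at the first non-significant result. Working back through 12, 6 and 3 months is one possible order.

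The statement should say that it covers the functional scores only. The MRI healing and fatty-degeneration analyses, which the Objective puts first, need their own rule.

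The change is to wording alone. It needs no extra patients or visits, and the 24-month test keeps its full α and power. The cost is that an isolated early difference, or a VAS difference, could be described but not claimed as confirmatory.

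### Normality of the data decides whether a mean difference or a rank ordering is tested against a target set in points, and the preoperative score is used only through a change score

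*Combined protocol and SAP*

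**What the plan says.** The Statistical analysis plan section is one paragraph. It takes its sizing from an earlier trial ("In a previous similar study, prior power analysis was performed to determine the study sample size"), which had 80% power at α .05 to "detect a minimum 5-point difference in the Constant score at the end of 2 years". That gave 47 per group with 10% loss, and the trial plans to follow more than 50 per group.

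The analysis itself is one sentence: "we compared the score improvement sequentially between the two groups", "using Mann-Whitney test or independent t test according to the normality". It names no normality test, no cut-off, and no score or visit at which normality is judged. It also names no effect measure and no confidence interval. The Methods section adds only that the parameters will be compared statistically.

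On data, Methods says that pain VAS and "other functional scores of the two group will be checked preoperatively and postoperative 3, 6, 12, 24 months". On allocation, it says only that "130 patients will be classified into two group"; the flow diagram is not shown in the text available.

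**The concern.** The two tests answer different questions. The independent t test addresses a difference in mean improvement. Mann-Whitney addresses whether values in one group tend to rank above those in the other, and it corresponds to a shift in points only if the two distributions have the same shape. The SAP fixes no distribution in advance, so the natural reading is that the collected data select the test. What the 2-year result speaks to is then known only after the data are seen.

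This matters here because the target is in points, and a p value from either test does not show whether the difference is near 5. Equal shapes also cannot be taken for granted. The Background describes a considerable failure rate after repair, and the Objective is to see whether PDRN affects healing. If it does, the groups may differ in the size of their lower tail.

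There is also a cost in efficiency. Preoperative scores are collected but enter only by subtraction, which is usually less precise than adjusting for them.

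**Working it through.** **Inputs from the documents:** 5 points, 80% power, α .05 (two-sided assumed), 47 per group, 10% loss, more than 50 followed per group (50 used below). **Not in the documents, so assumed:** SD, failure rates, score gap between failed and healed repairs, pre-post correlation, and the form of the normality check.

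**1. The sizing figure.** Without an SD, 47 cannot be reproduced, only back-solved.
- 47 evaluable per group: a t test has 80% power at a standardised difference of 0.584, so SD = 5/0.584 = 8.56.
- 47 including 10% loss: 47 × 0.9 = 42.3, so 42 evaluable; standardised difference 0.6186, so SD = 5/0.6186 = 8.08.

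At 50 per group, t-test power for 5 points is 82.4% (SD 8.56) or 86.5% (SD 8.08).

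**2. Effect of the rule.** Assumed rule: Shapiro-Wilk at .05 in each group, with failure in either group selecting Mann-Whitney.

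*Identical distributions, SD 8.3, 10,000 trials.* The rule rejects 4.8% (normal), 5.4% (mild skew) and 4.8% (marked skew). With normal data, 9-10% of trials still switch to Mann-Whitney by chance, with power essentially unchanged.

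*Failed-repair settings.* Score = N(0, residual SD), minus a gap if the repair failed. The whole control-group SD is held at the implied value, so residual SD = √(SD² − gap² × p(1−p)). For example, √(8.56² − 15² × 0.25 × 0.75) = √(73.27 − 42.19) = 5.58. Entries are t test / rule. Ranges span repeated runs of 4,000-5,000 trials; the Monte Carlo standard error near 5% is √(0.05 × 0.95/5,000) = 0.3 points.

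| SD; gap; failures | Residual SD | Equal means | Benefit only through fewer failures | Uniform 5-point shift |
|---|---|---|---|---|
| 8.56; 15; 25% vs 10% | 5.58 | 5.0-5.2% / 6.2-6.6% | 28% / 25% | 82% / 84% |
| 8.08; 15; 25% vs 10% | 4.81 | 5.2-5.4% / 7.0-7.3% | 33% / 26% | 87% / 90% |
| 8.56; 20; 10% vs 4% | 6.11 | 4.9-5.4% / 5.8-6.7% | 11-12% / 8-9% | 82-83% / 89-90% |

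The uniform shift uses the control failure rate in both groups. The benefit through failures is small in points (15 × 0.15 = 2.25; 20 × 0.06 = 1.2), hence the low power. The t test holds near 5% in all three settings without normal data. In the second setting, 86-88% of trials switch to ranks.

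These sizes are not bounds. With marked gamma skew (shape 2, SD 8.3), a uniform 5-point shift gives 84% / 94%. With that shape in one group only and equal means, rejection is 4.8% / 7.9%.

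**3. Baseline adjustment.** Assume normal data, equal pre and post SD σ, and correlation ρ. The change score has SD σ√(2(1−ρ)) and ANCOVA has residual SD σ√(1−ρ²). Their ratio, ANCOVA to change, is √((1+ρ)/2). Power is for 5 points at 50 per group.

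| ρ | 0.2 | 0.3 | 0.5 | 0.7 |
|---|---|---|---|---|
| 8.56 is the SD of change: ANCOVA residual SD | 6.63 | 6.90 | 7.41 | 7.89 |
| Power, ANCOVA / t test on change | 96 / 82% | 95 / 82% | 92 / 82% | 88 / 82% |
| 8.56 is the follow-up SD: ANCOVA residual SD | 8.39 | 8.17 | 7.41 | 6.11 |
| Change SD | 10.83 | 10.13 | 8.56 | 6.63 |
| Power, ANCOVA / t test on change | 84 / 63% | 86 / 69% | 92 / 82% | 98 / 96% |

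Simulation agrees: about 82% rising to 88-96% in the first case, and 64-97% rising to 83-99% in the second.

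**4. What an interval would show.** The 95% half-width for an unadjusted mean difference is 1.96 × SD × √(2/50): 3.2 points at SD 8.08 and 3.4 at 8.56. That is narrow enough to be informative against 5.

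**The case against.** Choosing between these tests by normality is common practice, and its operating characteristics here are mild. Type I error is near 5% when the distributions are identical, nothing changes with normal data, and power moves in both directions. All of this stands.

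The excess under equal means also needs a special arrangement. The better-healing group's failures must be offset exactly by lower scores in everyone else (2.25 or 1.2 points in the settings above), which is not a null of no treatment effect. A reader might infer that the rule materially inflates the false-positive rate. The documents do not support that. Larger excesses arise in constructed settings, such as a whole-group SD well above 8.1-8.6 or different distribution families in the two groups, and nothing in the plan points to either.

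The simulated normality check is an assumption, since the SAP could mean inspection or a judgement for each score. A missing confidence interval on its own would be missing detail rather than a wrong method. The Constant score at 24 months is what the sizing used, but the SAP does not name it as the analysed or primary endpoint.

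Baseline adjustment might be called a separate preference, because a fixed Welch t test already settles which quantity is tested. But the rule to be replaced is the whole analysis plan. A method that uses data already scheduled and is more precise in every case tabulated belongs in the replacement.

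**Conclusion.** The point holds as a matter of interpretability and efficiency. The plan leaves open whether its result is a mean difference or a rank ordering, although its only target is in points, and it uses the preoperative score only by subtraction.

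In the failed-repair settings at the implied SD, the rule adds about 1 to 2 percentage points to rejection under equal means and moves power by up to about 7 to 8 points either way. Adjusting for baseline is worth about 6 to 14 points of power if 8.56 is the SD of change. If it is the follow-up SD, the gain runs from about 2 points (ρ 0.7) to about 21 (ρ 0.2). These figures rest on the assumed rule, failure rates, gaps and correlations, and on a preoperative Constant score being among the functional scores collected.

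Two further inferences go beyond the text. One is that the same score would get different tests at different visits; the SAP does not say where normality is judged. The other is that 47 per group is wrong; without an SD it can be neither confirmed nor refuted. This should be corrected, but it does not by itself invalidate the trial.

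**What to change.** Delete the condition that makes the test depend on normality. Pre-specify one mean-difference analysis with a 95% CI for each score at each visit, including the Constant score at 24 months. The sponsor should confirm whether that is the endpoint intended.

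- **If allocation is random:** ANCOVA of the follow-up score on group and preoperative score, with robust standard errors.
- **If it is not:** a fixed Welch t test on improvement, which keeps the quantity the SAP states. ANCOVA could then change what is estimated. With a 5-point preoperative imbalance, equal mean improvement and equal pre and post SD, it would report (1−ρ) × 5 = 4.0, 3.5, 2.5 or 1.5 points at ρ = 0.2, 0.3, 0.5 or 0.7, while the change-score difference is 0.
- **In both cases:** Mann-Whitney with a Hodges-Lehmann shift and CI as a sensitivity analysis, reported whatever the data look like.

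The cost is a few sentences in the SAP and no new data, given the assumed preoperative score. The real downside is that, with a uniform shift and a heavy tail of failed repairs in both groups, an unadjusted mean comparison can lose power to the rank-based route: about 82-83% against 90% in the third setting above, and 84% against 94% under marked gamma skew.
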